1.5 Risk/Benefits

The most important potential risk is that participation in a study of neurotoxic sequelae to a chemotherapeutic regimen may increase anxiety about the therapy; this is especially true given the subjects will likely have recently learned of their cancer diagnosis and will have just been introduced to all the possible short-term and long-term risk of chemotherapy. Discussion of chemotherapy risk is part of a dedicated pre-therapy assessment and education visit ("pre-chemo visit") to place the risk of neurotoxicity within its appropriate context. This will also be discussed during recruitment and as part of the consent process. A potential benefit is the enhancement of opportunities to educate subjects regarding CIPN. Other risks include the discomfort of electrophysiologic evaluation, the time needed to complete questionnaires/ undergo neurologic examination, and loss of privacy relating to collection of study data.

Electrophysiologic evaluation of large fiber neuropathy is performed using nerve conduction studies (NCS) ; this is a test used routinely in the clinic for diagnosis of nerve disorders. Nerve conduction studies involve delivery of a mild electrical stimulation to the skin while recording the response from a superficial disc electrode placed over top of the skin. There is a risk of discomfort with the test but discomfort is generally mild and will be mitigated with careful study procedures. Evaluation of sudomotor function and small-fiber neuropathy is performed using SUDOSCAN, which may cause a slight tingling, but painless, sensation in the feet or the hands when the electrical impulse is being generated.

There is a risk of mild discomfort with placement of the paramagnetic material for EPR oximetry. The material is placed using a needle and syringe. In addition to the discomfort of the needle, there is a risk of minor swelling and discomfort after the injection (can persist for up to 3 days) and a chance of the India ink spreading, resulting in a larger dark spot than is expected. It should be noted that IRB approval has already been granted for the use of this technique in other applications (#16578 and #12459) and is in process of being approved for #29880 where these risks are detailed.

If a patient receives a PET/CT scan for restaging a tumor in the area of the injection, there may be a false positive at the site of the injection. Because this study does not involve ink injections into a tumor, this is suspected to be a very minimal risk.

Subjects will be protected against unnecessary risk with the use of careful study procedures. Records containing personally identifying information of subjects participating in the study will be coded and kept in a locked office in a secure environment. Access to code key will be limited to the PI and study coordinator. The risk of discomfort with the placement of the paramagnetic ink is minimal. Patients will be fully informed that the ink will make a permanent mark similar to a

small tattoo. The risk of breathing 100% oxygen through a nonrebreather mask for 10 minutes is minimal. The risk of discomfort with electrodiagnostic study will be minimized by performing a focused evaluation with the minimal number of electrical stimuli/needle electrode penetrations as possible and as per standard clinical practice.

Patients will be informed of any risk associated with blood draws which includes discomfort during the procedure, bruising, bleeding, swelling at the puncture site, infection, and feeling lightheaded or passing out during the procedure. Since blood will be generally drawn in conjunction with the patient's routine laboratory assessments for their chemotherapy, the additional risk should be minimal.

Patients will be informed of the risks of participating in research involving the study of their genetic information. The informed consent form will have an opt-in box ensuring that each patient is aware of the risks and research purposes of the blood draw and genetic analysis being conducted.

Patients will be informed that they may not personally benefit from participation in this study; however, the study aims to help patients in the future. The identification of a biomarker that not only provides information regarding the underlying pathophysiology, but also allows for early prediction of those patients at greatest risk of developing chemotherapy-induced peripheral neurotoxicity, is of significant benefit to patients undergoing chemotherapy. Early identification/prediction can help oncologists tailor and advise patients about side effects they may expect to develop and help them make informed choices about their therapy. Advancements in the understanding of the pathogenesis of this neurotoxicity will lead to better therapies, both in the prevention and the management of CIPN.

2 Study Objectives

The overall objective is to extend the pathophysiologic understanding of CIPN and identify better biomarkers for patients at greatest risk of developing early and/or severe or refractory CIPN.

Primary Objectives:

The primary objective of the study is: to prospectively compare peripheral tissue oxygenation response between patients who later develop CIPN, and those who do not.

Secondary Objectives:

The secondary objectives of the study are to: (i) establish the feasibility of the approach, (ii) to evaluate the utility of longitudinal clinical and electrophysiologic assessments and (iii) to describe changes in biomarkers of axonal degeneration including neurofilament light chain over the course of chemotherapy

Specific Aim #1: *Adapt the existing clinically established techniques for EPR oximetry to measurements of oxygen to be relevant to the pathophysiology of CIPN.* In the proposed research, we will use an India ink injection and obtain an initial oximetry reading assessing local oxygen metabolism. The objective of this aim will be to establish feasibility of the approach and obtain preliminary data for a more definitive and statistically robust cohort. Five measurements will be done within each study visit window to improve the strength of the readings.

Specific Aim #2: Establish a pre-exposure neurologic phenotype and baseline tissue oximetry in cancer patients scheduled to receive neurotoxic chemotherapy. In order to assess a potential biomarker for CIPN, it must be correlated to metrics of CIPN that can be reliably followed and quantitated as a function of progression and severity.

Specific Aim #3: Re-evaluate neurologic phenotype and tissue oximetry in symptomatic patients after exposure to a standard regimen of neurotoxic chemotherapy. Neurologic phenotype and EPR oximetry will be re-assessed at mid-chemotherapy treatment regimen or at the onset of symptoms. The assessments will be repeated at the completion of chemotherapy and will provide longitudinal data for comparison against baseline characteristics.

Specific Aim #4: In order to develop a proposal for a statistically robust cohort, use pilot data to (i) inform regarding the feasibility and potential utility of EPR oximetry as a CIPN biomarker, (ii) focus on the most sensitive metrics to follow, and (iii) to suggest trends of correlation in sub-metrics. This study is designed for the collection of preliminary data and to establish the feasibility and optimization of the EPR oximetric technique in CIPN. It is anticipated that this data will guide a larger study for which additional, external funding will be sought.

Specific Aim #5: Describe changes in serum NFL levels over the course of chemotherapy to determine if NFL can be used as a biomarker for axonal damage in patients who develop CIPN. NFL will be measured at baseline, before each round of chemotherapy and at the completion of chemotherapy. Changes in NFL will be compared between patients who develop CIPN and those that do not.

3 Study Design

3.1 General Design

This protocol is for a pilot study designed primarily to a) strengthen the evidence for using detailed clinical and electrophysiological characterization to predict the outcome and incidence of CIPN; b) obtain initial data evaluating the role of tissue oxygen as a potential biomarker for CIPN using EPR oximetry; and c) establish the feasibility of using EPR oximetry to correlate peripheral tissue oxygenation metrics with clinical and electrophysiological indices of CIPN. As a secondary objective, this pilot study will seek to demonstrate effective recruitment, screening, assessment, and retention in order to justify a larger trial in the future. The investigators will aim to enroll thirty (30) patients into the study over a one-year enrollment period. Subjects will have three study visits: Visit 1, before beginning chemotherapy treatment; Visit 2, mid-treatment; Visit 3, after completing chemotherapy. All subjects will undergo a neurologic evaluation and electrophysiological assessment in the form of nerve conduction studies and motor conductions at each study visit. Patients will have EPR tests at all study visits.

3.2 Primary Study Endpoints

The primary endpoint identified for the purposes of driving the sample size and primary analysis is: **the between-groups difference in longitudinal EPR oximetry measures by CIPN status.**

4 Subject Selection and Withdrawal

4.1 Inclusion Criteria

1. Scheduled to receive chemotherapy with taxane compounds for the treatment of breast cancer.
2. No prior taxane or platinum chemotherapy prior to enrollment.
3. Life expectancy greater than or equal to 12 months.
4. Able to provide independent informed consent for the study.
5. Able to undergo EPR oximetry
6. Age 18 years or older

4.2 Exclusion Criteria

1. Central nervous system or other impairments that interfere with clinical and electrophysiological assessment.
2. Unable to provide independent informed consent.
3. Pacemaker or other metallic objects that would be contraindicated for MRI.
4. A requirement for supplemental oxygen at baseline, or known, severe COPD.
5. Previous exposure to neurotoxic chemotherapeutic agents.

4.3 Subject Recruitment and Screening

Subjects will be recruited for the study by referral from their oncologist as soon as possible after the decision is made to proceed with taxane monotherapy for breast cancer, but before therapy is started. The oncologist will obtain the patient's consent to be contacted by our study team to explain the study. Informed consent will be obtained by the PI or designee. Potential subjects will be informed of the objectives and procedures of the study as well as adequately informed of the potential risks. Consent will be documented with the use of an IRB-approved consent document, and saved in the patient's electronic medical record.

4.4 Early Withdrawal of Subjects

4.4.1 When and How to Withdraw Subjects

Subjects will be withdrawn from the study if they are no longer able or willing to participate. If a participant is unable to continue with the study procedures or is deemed lost to follow up, the PI or designee will mail a signed letter to the patient to inform them of their withdrawal from the study. Subjects will be deemed lost to follow up if they fail to present for ongoing cycles of chemotherapy. If a subject declines additional cycles of chemotherapy or cannot complete the planned number of cycles, they will not be withdrawn, but a post chemo-therapy assessment will be performed. Subjects will be withdrawn if they develop an impairment that would interfere with clinical and electrophysiologic assessment.

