4.4.2 Data Collection and Follow-up for Withdrawn Subjects

Once a patient has been withdrawn from the study s/he will not be contacted by the research staff to conduct further assessments; however, survival data will be collected until one year after enrollment.

5 Study Device

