6.1 Schedule of Assessments

	Visit 1 (prior to beginning chemotherapy)	Visit 2 (mid-point of chemotherapy treatment or at onset of CIPN symptoms)	Visit 3 (one week or more after completion of chemotherapy)	Unscheduled EPR oximetry readings	Blood Draw Visits
Informed Consent	X				
Inclusion/Exclusion Criteria	X				
Neurological Exam	X	X	X		
Neurologic History	X				
Ink Injection	X				
Nerve Conduction Study	X	X	X		
Sudoscan	X	X	X		
EPR Oximetry Reading	X ¹	X ²	X ²	X	
Total Neuropathy Score	X	X	X		

Toronto Clinical Neuropathy Scoring System	X	X	X		
National Common Institute – Common Toxicity Criteria V.3	X	X	X		
Questionnaires- - McGill pain - Survey of Autonomic Symptoms - Subset of NQoL-DN - NTSS-6	X	X	X		
Blood Draw for Genetic Testing					X ³
Blood Draws for NF-L Assay					X ⁴

1. As many as 5 EPR measurements may be performed prior to beginning chemotherapy.
2. As many as 5 EPR measurements may be performed in the ±18 days surrounding the electrophysiologic assessments.
3. Blood for genetic testing can be drawn at any time during study participation.
4. Blood for NF-L testing will be drawn prior to the beginning of chemotherapy, prior to each scheduled chemotherapy treatment, and after the completion of chemotherapy.

6.2 Visit 1

Before beginning chemotherapy, and after providing informed consent, patients will receive an injection of India ink. Patients will then be scheduled to meet with a designated investigator for clinical assessments, which will occur prior to the start of chemotherapy. The neurologic assessment will include a standard neurologic history, neuropathy symptom questionnaire (NTSS-6 [Bastyr et al., 2005]), portions of the Total Neuropathy Score (TNS [Cornblath et al., 1999]), the National Common Institute – Common Toxicity Criteria V.3 (NCI-CTCv3), Toronto Clinical Neuropathy Scoring System, McGill pain questionnaire (Melzack, 1975), Survey of Autonomic Symptoms questionnaire, and a subset of a neuropathy-specific quality of life instrument (NQoL-DN, [Vinik et al., 2005]). As part of the neurologic examination, strength, sensation, and reflexes will be tested. Sensation testing may include pin, temperature, and vibration assessments using a Rydel-Seiffert tuning fork. Specific tests conducted will be at the discretion of the study neurologist. Assessments will be performed by one of the study neurologists.

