7.1 Sample Size Determination

This pilot study is designed for proof of concept and to establish the bedrock for a future trial with a more robust sample. The secondary objective of this pilot is to demonstrate effective recruitment, screening, assessment processes, and high participant retention. We will assess the proportion of potential participants that: meet inclusion criteria, consent to participate, and complete all assessments.

Thirty (30) patients will be enrolled in the study, and it has been estimated that ten (10) patients will develop CIPN during their taxane treatment. Accurate incidence of CIPN varies significantly; the average incidence is 70% (Seretny et al., 2014), with ranges from 30% to 90%. A conservative estimate is that 30%-50% of patients in this trial will develop symptoms of neuropathy during their chemotherapy treatment. Development of CIPN will be determined based on the results of their neurologic assessments. For data analysis, the patients will be divided by this CIPN status into two groups. Primary endpoints are continuous metrics: Endpoint 1) neurological phenotyping involves electrophysiological assessment (e.g. nerve conduction, EMG readings, SUDOSCAN results), and Endpoint 2) tissue oximetry involves the EPR measures). The mean levels of each electrophysiological or oximetry metric will be assessed between the two groups of patients (with CIPN vs. without) over time (at timepoints: before, mid-, and post-chemotherapy) using repeated measures ANOVA. This method will also assess the within-subject changes in the electrophysiological and EPR oximetry metrics over time, from baseline through post-chemotherapy, as well as the interaction between CIPN status and time. With 15 patients per group, we anticipate that we will have 80% power to detect a between-groups difference in longitudinal EPR oximetry measures by CIPN status of 28%, assuming a correlation of 0.5 among repeated measures, a standard deviation of 25%, alpha=0.05. The within-subjects and interaction tests are estimated to be able to detect an 8.5% change over time, with these same parameters (calculated using G*Power 3.1.9.2).

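### Section 4.4.1 withdraws subjects whose new impairment interferes with neurologic testing, so EPR readings that could still be taken are lost; the effect is small and mainly concerns subjects whose CIPN status is already known

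*Combined protocol and SAP*

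**What the plan says.** The last sentence of section 4.4.1 reads "Subjects will be withdrawn if they develop an impairment that would interfere with clinical and electrophysiologic assessment". It carries exclusion criterion 1 of section 4.2 ("Central nervous system or other impairments that interfere with clinical and electrophysiological assessment") forward into follow-up as a mandatory withdrawal rule. Under section 4.4.2 a withdrawn subject "will not be contacted by the research staff to conduct further assessments"; only survival is collected, to one year after enrollment. Neither section excepts EPR or NF-L. By contrast, section 4.4.1 keeps a subject who stops chemotherapy early and still performs the post-chemotherapy assessment.

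The primary endpoint in section 3.2 is "the between-groups difference in longitudinal EPR oximetry measures by CIPN status". EPR is a session of about 30 minutes in Radiation Oncology (sections 6.2 and 6.3), and nothing in the text makes it depend on nerve conduction testing. NF-L needs a blood sample, taken with clinical draws where possible (section 6.6).

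For the grouping variable, section 7.1 says "Development of CIPN will be determined based on the results of their neurologic assessments". It plans repeated measures ANOVA over three timepoints and states neither a missing-data rule nor a dropout allowance.

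**The concern.** The rule ends the primary measurement because a different measurement has become difficult. A subject found to have CIPN at Visit 2 who then develops another disabling impairment already has a group. A Visit 3 EPR reading from that subject could enter the primary comparison directly, yet it would not be taken. With 30 patients and about ten CIPN cases expected, each such reading has some value, and section 7.1 makes retention and complete assessment objectives in their own right.

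The analysis can add to the loss. In its conventional complete-case form, repeated measures ANOVA drops a subject with no Visit 3 altogether, so the Visit 1 and Visit 2 readings already collected also leave the test.

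**Working it through.** **Inputs from section 7.1.** Difference 28%, SD 25%, correlation 0.5, alpha 0.05 (taken as two-sided), three timepoints, 30 patients, ten expected with CIPN, hence 10 vs 20. **Assumed, not in the documents:** k = 1, 2 or 3 of the ten CIPN patients lack Visit 3 only.

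**The plan's own figure.** Section 7.1 states 80% power at 28% with 15 per group. The SD of a three-visit mean is 25 × √((1 + 2 × 0.5)/3) = 20.41. At 15 vs 15 the standard error is 20.41 × √(1/15 + 1/15) = 7.45, the noncentrality (28/7.45)² = 14.1, and power from F(1, 28) is 95.2%. The stated 80% therefore does not reproduce. A single-timepoint t-test at 10 vs 20 comes close (79.7%), but that is not the stated design. This is a separate matter. It does mean that the powers below should be compared with one another and not with the plan's 80%.

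**Average group difference, incomplete cases dropped.** SE = 20.41 × √(1/n₁ + 1/20), with n₁ + 18 denominator degrees of freedom.

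| CIPN patients without Visit 3 | n₁ | SE | Power at 28% |
|---|---|---|---|
| 0 | 10 | 7.91 | 92.8% |
| 1 | 9 | 8.19 | 90.9% |
| 2 | 8 | 8.54 | 88.4% |
| 3 | 7 | 8.96 | 85.1% |

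If the same numbers were lost from the non-CIPN group, power would be 92.3%, 91.7% and 91.1%.

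**Average group difference, all visits kept.** This uses generalised least squares with compound symmetry, group-by-time means, variance treated as known and 28 degrees of freedom. Information per subject on the average is 3/(625 × 2) = 0.00240 with three visits and 2/(625 × 1.5) = 0.00213 with two. The ratio is 0.889, so a two-visit subject keeps 89% of the information. The SE is 7.906, 7.938, 7.979 and 8.030 for k = 0 to 3, and power is 92.8%, 92.6%, 92.3% and 92.0%.

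**Group difference in Visit 1 to Visit 3 change.** With full data, SE = 25 × √(2 × (1 − 0.5)) × √(1/10 + 1/20) = 9.68.

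| k | Mixed model SE (increase) | Complete-case SE (increase) |
|---|---|---|
| 1 | 9.92 (2.4%) | 10.03 (3.6%) |
| 2 | 10.21 (5.4%) | 10.46 (8.0%) |
| 3 | 10.56 (9.1%) | 10.98 (13.4%) |

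Most of the loss in power for the average difference comes from the handling of incomplete cases, and a mixed model removes it. The loss of information on change remains in the mixed model; taking the Visit 3 reading is what restores it.

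**The case against.** The rule has a rationale. CIPN status and the within-timepoint correlations in section 7.1 both need the neurologic assessments. An EPR reading with no such assessment beside it cannot enter those correlations, and it helps the group comparison only if status is already settled. The rule also mirrors exclusion 1, and section 7.1 gives priority to metrics at the pre- and mid-chemotherapy timepoints, which would usually have been collected already. All of this stands. It narrows the point to subjects with established status and keeps the size small, but it does not explain why EPR must stop for them.

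The NF-L part is weaker still. Section 1.1 says NF-L is raised in CNS disorders, and CNS impairment is the one kind of impairment that exclusion 1 names. Samples taken after a new CNS impairment could not fairly enter the Aim 5 comparison, so the gain is limited to other impairments.

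The illustration is also one-sided, because it places every loss in the CIPN group, and no withdrawal rate is documented.

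Four stronger readings are tempting, and the documents do not support them.

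- *Severe CIPN itself triggers withdrawal, which would make the loss depend on outcome.* Section 2 sets out to "identify better biomarkers for patients at greatest risk of developing early and/or severe or refractory CIPN", and Aim 3 is to "Re-evaluate neurologic phenotype and tissue oximetry in symptomatic patients". CIPN is clearly not the intended trigger; section 4.4.1 simply does not say so.
- *One untestable nerve forces withdrawal.* Section 6.2 says "Specific tests conducted will be at the discretion of the study neurologist", so a substitute test can be chosen. The rule applies when the assessment as a whole is impaired.
- *Data collected before withdrawal are discarded.* Neither 4.4.1 nor 4.4.2 says this. Earlier visits would be lost only through a complete-case analysis.
- *The study's power is in jeopardy.* Repeated-measures power stays at 85.1% or more in every case shown.

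**Conclusion.** The point holds in a limited form. Sections 4.4.1 and 4.4.2 together give up later EPR readings that may still be obtainable, and those readings would be useful mainly for subjects already classified as CIPN. On the assumed 1 to 3 losses at 10 vs 20, the cost is about 2 to 8 percentage points of power if incomplete cases are dropped (92.8 − 90.9 = 1.9; 92.8 − 85.1 = 7.7). It is less than 1 point in a mixed model (92.8 − 92.0 = 0.8), with a 2.4% to 9.1% larger standard error for change to Visit 3. These figures rest on the plan's SD and correlation, on compound symmetry and on an assumed number of losses; the true frequency cannot be estimated from the documents. The change is worth making because it is cheap, not because the effect is large.

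**What to change.** **Section 4.4.1.** Replace the last sentence with: *If a subject develops an impairment that prevents some or all of the clinical or electrophysiologic assessment, the affected tests are omitted and the reason recorded; EPR, NF-L sampling and any assessable components continue while the subject remains able and willing. CIPN of any severity is not a reason for withdrawal.* The sentence on notifying participants who cannot go on with study procedures should be limited to those who can undergo none of the remaining procedures. Otherwise it could still withdraw the same subjects.

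**Section 7.1.**

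1. Analyse all available timepoints with a linear mixed model instead of repeated measures ANOVA.
2. Keep as CIPN anyone already positive at an earlier assessment.
3. For subjects last assessed as negative who then become unassessable, run a sensitivity analysis: as non-CIPN, as CIPN, and excluded.
4. Flag NF-L samples taken after a new CNS impairment and exclude them from the Aim 5 comparison.

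**Cost.** Two edits in 4.4.1, a short paragraph in 7.1 and a flag on the NF-L sample record. The downsides are the burden of EPR visits for a few impaired patients (up to five sessions of about 30 minutes per window), some incomplete visits and slightly more analysis. The able-and-willing condition limits the burden. Whether subjects should be re-screened for safety before later EPR sessions is a separate matter.
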